### **Sample size calculation**

The sample size for this intervention-based study was calculated using R Studio to ensure adequate power in the detection of potential statistically significant effects.

Considering a multi-level design nesting center, PE teacher and group, the sample size calculation was grounded on an anticipated effect size of 0.5, reflecting a moderate impact of the intervention. The power of the study was set at 80% with a significance level (alpha) of 0.05, aligning with common practices in educational research (McConnell et al., 2019).

Acknowledging the inherent structure of this study, an Intra-Class Correlation (ICC) of 0.1 was assumed based on similar educational settings (Hedges & Hedberg, 2007). This ICC estimate accounted for the expected homogeneity within the three levels (class group within PE teacher, PE teacher within center). To accommodate potential participant dropout, particularly among students, we incorporated a 40% anticipated dropout rate into our calculations (e.g., Meerits et al., 2022). The minimum sample size was adjusted to 210 students across 15 PE teachers, averaging 14 students per teacher. This adjustment ensures that our study maintains sufficient statistical power even in the face of anticipated losses, thereby safeguarding the integrity and validity of our findings.

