### ***Participants and recruitment***

At least 16 secondary PE teachers, eight in the experimental group and eight in the control group, along with their respective students, will be expected to participate in this study. The maximum number of participating teachers will be capped at 20, due to the limited human resources of the research team. PE teachers will select at least two classroom groups comprising at least 14 students each to invite to participate in this study. Eligible students will be those aged 12 to 17 years in secondary schools. Participation will be voluntary and anonymous.

Various social media platforms (i.e., Instagram, Twitter, and WhatsApp) and other communication methods (i.e., email) will be used for teachers' recruitment. An informative poster will be launched, detailing the target sample, content, aims, and training program dates. This poster will also include two links (QR code): one with a document providing further information and another to registration through a brief Google Forms questionnaire. Regarding the additional information document, it is important to note that it will detail a more comprehensive overview of the objectives, the different phases of the program, inclusion criteria, the requirements that each teacher must accept to participate, and the

teaching skills that will be developed during the training program. Teachers with further inquiries can contact the research team via email or phone. The registration period will last approximately 21 days.

Once the interested PE teachers have registered, various inclusion criteria will be considered for the final selection: 1) Being an in-service PE secondary school teacher for the entire academic year; 2) Attending 100% of the training program sessions; 3) Fill in a short questionnaire at the end of each session of the training program, as well as fulfilling questionnaires of the study variables three times; 4) Allowing the recording of two PE lessons; 5) Participating in two focus groups, one at the end of the training program and one at the end of the study, and 6) Not participating in other training sessions related to PE instruction during the program. Moreover, the inclusion criteria for students will be: 1) Authorization from parents or legal guardians; 2) Completion of questionnaires of the study variables three times; 3) Regular participation in PE lessons.

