### ***Analysis plan***

#### ***Quantitative analyses***

Firstly, the effects of the four sessions of the training program on the study variables assessed in teachers will be examined. The overall mean for each of the 11 variables perceived by PE teachers about the quality of the training program (e.g., interaction, innovation, interest, intelligibility, etc.) will also be calculated, representing the mean across the different sessions. A repeated measures analyses of variance (ANOVA) will be used to assess PE teachers' global appreciation of 11 variables related to the quality of the training program (e.g., interaction, innovation, interest, intelligibility, etc.) across the sessions of the training (i.e. within-subject analyses). Accordingly, each of the training sessions will be introduced as an independent variable (i.e. within-subject factor) and repeated measures of the PE teachers-related variables will be entered sequentially as dependent variables.

Secondly, the effects of the intervention implementation in PE lessons on study variables for both teachers and students will also be examined. Levene and Kolmogorov–Smirnov tests will be used to ensure the equality of variances and normal data distribution, respectively ( $p > .05$ ). Cronbach's coefficient will be calculated for each study variable across the three measurements. To examine the effects of the intervention on study variables, a  $3 \times 2$  (time x condition) repeated measures multivariate analysis of covariance (MANCOVA) will be performed for both teachers and students. Age, gender, teaching experience, type of school (public or private), and school location (rural or urban) will be introduced as covariates among teachers, while age, gender, and school grade level will be introduced as covariates among students. Subsequently, to examine intragender differences of the intervention on study variables, a  $3 \times 2 \times 2$  (time x condition x gender) repeated measures MANCOVA will be performed for both teachers and students. The same covariates will be entered as previously analysis, excluding gender. Multiple paired t-tests with Bonferroni correction will be calculated to determine between-group (i.e., experimental-control group) and within-group (i.e., pre-post) differences. Cohen's criteria will be used as indicators of small (.01), moderate

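### On its own inputs (effect 0.5, ICC 0.1, 40% dropout), the minimum of 210 students across 15 teachers gives about 50–57% power without baseline adjustment, not 80%

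*Protocol*

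**What the plan says.** The Protocol, under *Sample size calculation*, gives every input of a cluster-trial calculation:

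- Effect: "the sample size calculation was grounded on an anticipated effect size of 0.5, reflecting a moderate impact of the intervention".
- Error rates: "The power of the study was set at 80% with a significance level (alpha) of 0.05".
- Clustering: "an Intra-Class Correlation (ICC) of 0.1 was assumed based on similar educational settings". The section says this covers class groups within teachers and teachers within centres, with no split by level.
- Losses: "we incorporated a 40% anticipated dropout rate into our calculations".
- Result: "The minimum sample size was adjusted to 210 students across 15 PE teachers, averaging 14 students per teacher".
- Assurance: "This adjustment ensures that our study maintains sufficient statistical power even in the face of anticipated losses".

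Under *Context, design, and randomization*, teachers are randomised and each school takes part in one arm only. Under *Participants and recruitment*, at least 16 teachers are expected, eight per arm, each inviting at least two class groups of at least 14 students. The same section sets an upper limit: "The maximum number of participating teachers will be capped at 20, due to the limited human resources of the research team". Under *Quantitative analyses*, a time × condition "repeated measures multivariate analysis of covariance (MANCOVA) will be performed for both teachers and students".

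**The concern.** Since teachers are randomised, an ICC of 0.1 and a 40% loss should both raise the number required. Yet 210 is exactly what an individually randomised trial would need for the same effect once 40% loss is allowed for. If the clustering was left out, the stated minimum does not carry the stated power.

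This is the Protocol's only justification of its size. A null result in the students (hypothesis H3) would be read as coming from a trial with an 80% chance of detecting a moderate effect, when the stated inputs support a chance close to one half.

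**Working it through.** **Inputs.** From *Sample size calculation*: d = 0.5 (SD = 1), alpha 0.05, power 80%, ICC 0.1, dropout 40%, 15 teachers, 14 students each. From *Context, design, and randomization*: the teacher is the randomised unit. Assumed because the Protocol does not say: two-sided test, all of the ICC at teacher level, loss spread evenly over students, no baseline adjustment. Arms are 7 and 8 teachers for 15, and equal otherwise.

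**Step 1: reproduce 210.** Without clustering, n per arm = 2 × (1.960 + 0.842)² / 0.5² = 62.8, so 63, or 126 in total. Then 126 / (1 − 0.4) = 210 exactly. The t-based total of 128 gives 214, so the match is to the normal formula only. Another route also gives 210: 15 × 10 × 1.4.

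**Step 2: the requirement with clustering.** The design effect is DE = 1 + (m − 1) × 0.1. With m = 14 × 0.6 = 8.4 retained per teacher, DE = 1.74. The requirement is 126 × 1.74 = 219 analysed, and 219.2 / 0.6 = 365 recruited.

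**Step 3: power of the stated minimum.** Effective n = 15 × 8.4 / 1.74 = 72.4. The standard error is √[1.74 × (1/(7 × 8.4) + 1/(8 × 8.4))] = 0.236, and 0.5 / 0.236 = 2.12. Power is Φ(2.12 − 1.96) = 57% by the normal approximation, or 50% by the noncentral t with 13 df. A simulation (20,000 runs, 40% random loss, t-test on teacher means) gave 49%.

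**Step 4: other configurations** (normal / t with K − 2 df):

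| Teachers × students analysed | DE | Effective n | Power | Detectable d at 80% |
|---|---|---|---|---|
| 15 × 8.4 (stated minimum after loss) | 1.74 | 72.4 | 57% / 50% | 0.66 / 0.71 |
| 15 × 10 (the other route to 210) | 1.90 | 78.9 | 60% / 54% | – |
| 15 × 14 (no loss) | 2.30 | 91.3 | 66% / 60% | 0.59 / 0.64 |
| 16 × 8.4 (14 enrolled, after loss) | 1.74 | 77.2 | 59% / 53% | 0.64 / 0.69 |
| 20 × 8.4 (14 enrolled, after loss) | 1.74 | 96.6 | 69% / 64% | 0.57 / 0.60 |
| 16 × 16.8 (28 enrolled, after loss) | 2.58 | 104.2 | 72% / 66% | 0.55 / 0.59 |
| 20 × 16.8 (28 enrolled, after loss) | 2.58 | 130.2 | 81% / 77% | 0.49 / 0.52 |

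**Step 5: teachers needed.** At 8.4 retained per teacher, 80% power needs about 26 teachers (normal) or 28 (t; 30 if arms must be equal and 80% fully reached).

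**Step 6: sensitivity at 15 × 8.4** (normal / t):

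- ICC 0.05: 67% / 60%. ICC 0.20: 43% / 38%.
- ICC split as 0.05 for teacher and 0.05 for class, two classes per teacher: 62% / 55%. All 0.1 at class level: 68% / 62%.
- One-sided alpha 0.05: 68% / 64%.
- Baseline as a covariate, variance multiplied by (1 − r²) with the same r at student and teacher level: r = 0.5 gives 69% / 62%, r = 0.7 gives 84% / 78%. Reaching 80% needs r of about 0.65 / 0.71.

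**The case against.** The best case for the plan has four parts.

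- **The ICC need not sit at teacher level.** The Protocol spreads it over nested levels without a split, and the test's sidedness is not stated either. This stands as a limit on precision: 50–57% is the low end of what the text allows. The more favourable readings after 40% loss, taken one at a time, still stop at 68%. Taking 30 class groups of 7 as independent clusters gives 82% / 79%, but it ignores teacher-level randomisation, the dropout allowance and the class size of at least 14. With dropout restored it gives 69% / 66%. This route does weaken the inference that the ICC was never used.
- **The analysis uses the T1 measure.** A strong enough baseline correlation would restore 80%. However, the sample size section states no correlation, so the 80% cannot be credited to one.
- **Actual recruitment may exceed the minimum.** At least 16 teachers are planned, and the 28 or more students per teacher are invited, not enrolled. If exactly 28 enrol, 16 teachers still fall short. The cap of 20 reaches 80% only by the normal approximation. None of this supports the figure for 15 teachers and 210 students.
- **The remedy is only a rewording.** That is true, but the sentence being reworded is the power claim on which the trial's size rests.

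**Conclusion.** The concern holds. The stated minimum does not deliver 80% power on the stated inputs. With teachers as clusters, two-sided testing, 40% student loss and no baseline adjustment, power is 50–57% for an effect of 0.5. No reading examined that keeps the 40% loss and adds no baseline correlation brings 15 teachers with 14 students each to 80%.

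That clustering was left out is an inference from 126/0.6 = 210. The shortfall does not depend on it. Unequal numbers per teacher or the loss of a whole teacher would lower power further, and teachers sharing a school would not raise it. Because the Protocol offers this figure as assurance, it must be corrected.

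**What to change.** In *Sample size calculation*, delete the statement that 210 students across 15 teachers keep the planned power after losses. Replace it with the power, or the detectable effect, for the 16 to 20 teachers in *Participants and recruitment*, with the design effect applied after dropout. State the level at which the ICC of 0.1 applies, whether the test is two-sided, and how many students per teacher are expected to enrol rather than only how many are invited. If the baseline score is relied on for precision, give the assumed correlation and its source.

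For reference, without baseline adjustment and after 40% loss, 14 enrolled per teacher gives about 53–59% at 16 teachers and 64–69% at 20.

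The cost is rewriting one section and accepting a less favourable stated power. Recruitment, the teacher cap and the analysis need not change.

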### ***Participants and recruitment***

At least 16 secondary PE teachers, eight in the experimental group and eight in the control group, along with their respective students, will be expected to participate in this study. The maximum number of participating teachers will be capped at 20, due to the limited human resources of the research team. PE teachers will select at least two classroom groups comprising at least 14 students each to invite to participate in this study. Eligible students will be those aged 12 to 17 years in secondary schools. Participation will be voluntary and anonymous.

Various social media platforms (i.e., Instagram, Twitter, and WhatsApp) and other communication methods (i.e., email) will be used for teachers' recruitment. An informative poster will be launched, detailing the target sample, content, aims, and training program dates. This poster will also include two links (QR code): one with a document providing further information and another to registration through a brief Google Forms questionnaire. Regarding the additional information document, it is important to note that it will detail a more comprehensive overview of the objectives, the different phases of the program, inclusion criteria, the requirements that each teacher must accept to participate, and the

teaching skills that will be developed during the training program. Teachers with further inquiries can contact the research team via email or phone. The registration period will last approximately 21 days.

Once the interested PE teachers have registered, various inclusion criteria will be considered for the final selection: 1) Being an in-service PE secondary school teacher for the entire academic year; 2) Attending 100% of the training program sessions; 3) Fill in a short questionnaire at the end of each session of the training program, as well as fulfilling questionnaires of the study variables three times; 4) Allowing the recording of two PE lessons; 5) Participating in two focus groups, one at the end of the training program and one at the end of the study, and 6) Not participating in other training sessions related to PE instruction during the program. Moreover, the inclusion criteria for students will be: 1) Authorization from parents or legal guardians; 2) Completion of questionnaires of the study variables three times; 3) Regular participation in PE lessons.

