## **Materials and methods**

### ***Context, design, and randomization***

[figure not shown]
This study will be carried out in a northeast region of Spain [details masked for review process]. PE is mandatory for every secondary school student in Spain. Each student receives two 50-minute coeducational PE lessons per week. Spanish Secondary PE teachers are expected to teach between 18 and 21 hours per week. Typically, the annual teaching plan of PE teachers includes approximately six to eight distinct teaching units per year. These units encompass various content types such as individual, cooperative, and interactive sports and games, as well as body expression, health-related fitness, and outdoor activities, all of which are outlined in the PE curriculum. The academic year lasts from September to June, divided into three terms, each separated by a holiday period (i.e., Christmas and Easter).

A randomized controlled trial design with a mixed-method approach will be carried out. PE teachers agreeing to participate in the trial will be randomly assigned to either the experimental or the control group. Randomization will be conducted using the digital tool available at <https://echaloasuerte.com/>. To prevent contamination of the experimental condition, schools will only participate in one group (i.e., experimental or control). Subsequently, at least two groups of students from each PE teacher will be randomly selected.

This study will comprise two phases: 1) a teacher-training phase and 2) an implementation phase with students. It should be noted that the training program will continue with some individual and group sessions during the implementation phase. Since teachers' and students' perceptions of (de)motivating teaching styles and approaches and other study variables require several months for greater accuracy in their perceptions, the

training program will not start until the second term of the academic year (for more details see Figure 1).

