## ***Measures***

### ***Questionnaires***

The following PE teachers' variables will be measured using Google Forms before the training program (T1), as well as during (T2) and at the end of the implementation of the intervention with their students (T3) (see Figure 1):

**Socio-demographic variables.** Age, gender, teaching experience, type of school (public or private), and school location (rural or urban) will be self-reported by teachers.

**(De)motivating teaching styles and approaches towards students.** To assess self-reported (de)motivating teaching styles toward students, the Spanish version of the SIS in Physical Education (SIS-PE; (Burgueño, Abós, et al., 2024) will be used. The SIS-PE comprises 12 typical teaching situations consisting of four items each (i.e., 48 items). Autonomy-supportive items are categorised into participative (four items) and attuning (eight

items) approaches. Structure items are operationalised into guiding (seven items) and clarifying (five items) approaches. Control items are divided into demanding (seven items) and domineering (five items) approaches. Chaos items are operationalised into abandoning (eight items) and awaiting (four items) approaches. For instance, this situation “At the start of class...” is followed by four items: you can explore students’ prior knowledge of the topic (attuning), set up a class clearly and straightforwardly (clarifying), demand application of what’s taught (demanding), or just begin and let the class evolve (awaiting)”. It should be noted that, since teachers’ perceptions of their (de)motivating teaching styles could be different according to the classroom group, teachers will have to answer the questionnaire taking into account the groups of students selected for the study. Teachers’ responses will be assessed using a 7-point Likert scale ranging from 1 (“Does not describe me at all”) to 7 (“Describes me perfectly”).

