### **Control group**

Control group teachers will not initially receive the training program and, as a result, will not intentionally implement any motivational strategy. They will only complete the questionnaires at the same times as experimental group teachers (See Figure 1). Control group teachers will receive the training program after the last study measurement, as well as an extensive final report on their teaching profile, and a series of motivational strategies aimed at enhancing their (de)motivating teaching style.

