be considered. Secondly, observation will be used twice to ensure intervention fidelity and provide constructive feedback to teachers during the intervention but will not be used as a complementary measure of students' and teachers' perception of (de)motivating teaching styles in the three measures of the study due to lack of human resources. Thirdly, teachers' perceptions of their beliefs regarding (de)motivating teaching styles will not be assessed by means of questionnaires due to their length, as well as the absence of validated instruments of control and chaos styles. Additionally, relatedness satisfaction and frustration at work will not be assessed because the training program will not target teachers within the same school. Additionally, teachers' perceptions of depersonalization and reduced personal accomplishment (i.e., burnout factors) will not be assessed using questionnaires due to their length. However, all these variables will be assessed through the focus groups to obtain more information on the effects of the training program and the subsequent intervention carried out. Finally, students' perceptions of relatedness satisfaction and frustration in PE will not be assessed employing questionnaires due to their length and because the teacher training program was based on the circumplex model, which does not address the need for relatedness. As a final limitation, it is very likely that a post-intervention follow-up measure cannot be carried out the following academic year because in Spain it is very common for teachers to change schools every year. Therefore, it will only be possible to assess students' perception of the study variables if the teacher is the same. Similarly, the perception of (de)motivating teaching style might change with different classroom groups.

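### The protocol says both that study classes are drawn at random and that teachers choose them, and it does not fix the classes before teachers learn their arm

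*Protocol*

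**What the plan says.** Teachers are the allocated unit (Protocol, Context, design, and randomization): "PE teachers agreeing to participate in the trial will be randomly assigned to either the experimental or the control group". On procedure, that section gives only "Randomization will be conducted using the digital tool available at", followed by a web address, and the condition that each school takes part in one arm only. It then continues: "Subsequently, at least two groups of students from each PE teacher will be randomly selected".

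Participants and recruitment describes the same step differently: "PE teachers will select at least two classroom groups comprising at least 14 students each to invite to participate in this study". It gives no date for that choice.

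The Questionnaires section links the chosen classes to the teacher outcome. Because a teacher's view of his or her own style "could be different according to the classroom group, teachers will have to answer the questionnaire taking into account the groups of students selected", the classes must be known by the first measurement (T1). The account of the first training session also presupposes known study classes, since teachers are asked there which units they still have to teach in them.

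**The concern.** Both sentences settle how the minimum of two classes per teacher is reached. One leaves it to chance, the other to the teacher. A team that followed one would breach the other.

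The second rule matters because teachers cannot stay blind to their arm: experimental teachers attend training, while controls wait until after the last measurement. If a teacher chooses classes knowing the arm, the student sample is selected after randomisation by someone with an interest in the result. Randomising teachers then no longer guarantees comparable students in the two arms. The teacher self-reports are affected too, because they are answered with those classes in mind. The student hypothesis (H3) and the teacher hypothesis (H2) are therefore both exposed.

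The protocol already guards against teacher influence on student data by keeping the teacher out of the room while questionnaires are completed. Letting the same teacher decide who is asked sits poorly with that safeguard.

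**Working it through.** No figure in the plan is in dispute, so the check is a comparison of the text, followed by a count of what is exposed.

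**1. Do the two sentences concern the same step?** Yes. Both set at least two classes per teacher for the study. A reconciling reading is conceivable, in which teachers nominate a pool and the team draws from it, but no section states it. The recruitment sentence has teachers selecting the classes that are to be invited, which reads as the final choice.

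**2. What does the text say about timing?**
- Context, design, and randomization places class selection after allocation.
- Participants and recruitment does not date the teachers' choice.
- Questionnaires implies that classes are known by T1.
- No section says when teachers learn their arm, that allocation is concealed, or that classes are fixed beforehand.

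**3. What follows under each reading?**

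| Who selects | When | Consequence |
|---|---|---|
| Random draw from all eligible classes | Before or after allocation | Knowledge of the arm cannot steer which classes enter |
| Teacher | Before the arm is known | Choice may be unrepresentative but cannot depend on the arm |
| Teacher | After the arm is known | Choice can differ between arms, so post-randomisation selection is possible |

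The text excludes none of the three rows. Only the third threatens the comparison between arms.

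**4. Would the planned analysis remove the problem?** Only in part. T1 scores in a time-by-condition analysis address differences in starting level. Beyond that, the student model adjusts for little: "while age, gender, and school grade level will be introduced as covariates among students". How receptive a class is, or how it would have changed over the year anyway, is not captured.

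**5. How much of the trial is exposed?** Inputs from Participants and recruitment: at least 16 teachers (8 per arm), at most 20, at least 2 classes each, at least 14 students per class.
- Minimum number of teachers: 16 × 2 = 32 classes; 32 / 2 = 16 per arm; 32 × 14 = 448 students invited.
- Maximum number of teachers: 20 × 2 = 40 classes; 40 × 14 = 560 students invited.
- Weight of one class in its arm with 16 equal classes: 1 / 16 = 6.25%.

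Class and student counts are lower bounds in both cases, because classes per teacher and students per class are both stated as minimums. They measure exposure, not bias. The document gives no input from which a bias could be calculated.

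**The case against.** The strongest reply is that the harmful scenario is assembled from two halves. It takes teacher choice from one section and post-allocation timing from the other, and neither section states both. A random draw after allocation is harmless, and a teacher's choice during recruitment might precede allocation. This is fair, and it is why unblinded choice can only be called permitted, not planned. It does not remove the contradiction, and nothing in the text rules the combination out.

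Second, Figure 1, the timeline, was not available for this review and might show some timing. Its caption covers the training program and data collection, and no text refers to it for who selects classes. It could narrow the timing question but would not reconcile the two sentences.

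Third, the remark in Limitations that "the perception of (de)motivating teaching style might change with different classroom groups" arises when discussing follow-up in the next academic year, not selection within the trial. That is correct. It supports the general idea only, and the statement in Questionnaires carries the point without it.

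Fourth, T1 measurement and the covariates give partial protection, and the direction of any bias is open. Both stand. Controls also have a stake in their classes, since "Control group teachers will receive the training program after the last study measurement, as well as an extensive final report on their teaching profile". Teachers in either arm might prefer easy or difficult groups.

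**Conclusion.** The concern holds. The contradiction over who selects the classes is explicit and can be stated with high confidence. The absence of any rule fixing classes before disclosure rests on the visible text, without Figure 1.

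The consequence is conditional. If teachers choose, if they know their arm when they do, and if their choices differ between arms, the between-arm comparisons of student outcomes and of teachers' self-rated style may be biased. The document does not show that this would happen, and neither size nor sign can be estimated. The point should be corrected because a stated procedure, followed literally, leaves the composition of the entire student sample to unblinded teachers. It is not a detail to leave to an analysis plan: who selects participants, and when, is a protocol procedure.

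**What to change.** Replace the teacher-selection sentence in Participants and recruitment with one rule that agrees with Context, design, and randomization. For example: each registered teacher lists all eligible classes of at least 14 students; the research team draws at least two per teacher at random; the drawn classes are fixed before the teacher is told the assigned group. Add the last clause to Context, design, and randomization as well. The present order there, teachers randomised and then classes drawn, can stay if the arm is disclosed only after the draw.

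As an optional further safeguard, where the schedule allows, invite students and complete T1 before disclosure. The main correction does not depend on this.

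The cost is a wording change in two sections, one class list per teacher (which the existing registration form can collect) and at most 20 short draws. Teachers lose the freedom to pick convenient classes, and learn their arm slightly later. Under the optional step, all teachers would have to keep the four weekly training dates free until after T1 without knowing their arm.
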